11.7 Constipation severity - Bespoke CYPHP Constipation Score

Completed by: parent/carer of CYP with constipation

Participants are split into 2 groups:

- Toilet trained (TT) children - 7 questions.
- Non-TT children – omit final 2 questions; 5 questions posed.

Scoring is the same, regardless of group:

Q1: How often does your child open their bowels?

- 0 points if answer 3+ times/week
- 2 points if answer Twice or less

Q2-Q7, answers and points ():

- Never (0)
- Occasionally (1)
- At least once (2)

Scoring criteria for Health Check Triage: Points are summed from all completed questions.

The Bristol Stool chart is also displayed and participants are asked to identify their child's usual stool type (from 1 to 7). This is not used for scoring the questionnaire but will be summarised as a separate outcome measure.

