11.9 Analysis Methods

Analysis (for 6-month and 12-month follow-up): Random-effects regression models. Covariates at individual level: participant age group, sex, IMD 2015 quintile, IDACI 2015 quintile, Borough, and the baseline questionnaire outcome score. Covariates at cluster level: mean IMD 2015, mean IDACI 2015, number of children under 16 years, rate of paediatric OP referrals 2015-16, and the mean baseline questionnaire outcome score.

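### The SAP gives the constipation measure no outcome score apart from the triage sum, and that sum runs on different scales for the 5-question and 7-question forms

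*SAP*

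**What the plan says.** SAP section 11.7 splits the children with constipation into two groups. One is "Toilet trained (TT) children - 7 questions". The other is described as "Non-TT children – omit final 2 questions; 5 questions posed". Points per answer do not differ between them: "Scoring is the same, regardless of group". Q1 scores 0 or 2 ("2 points if answer Twice or less"), and each of Q2-Q7 scores 0, 1 or 2.

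The one rule for the total is that "Points are summed from all completed questions". The same line introduces it as the criterion for Health Check triage. Section 11.7 gives no other rule for the total, whether for analysis, for the difference between forms or for unanswered items.

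The score is also an outcome. Section 9.2 lists it as item 11, Table 1 in section 6.4 repeats it at 6 and 12 months, and section 15 includes it in the equity analyses. Section 11.9 analyses participant-reported outcomes by random-effects regression, with individual-level covariates that include age group and "the baseline questionnaire outcome score". Neither toilet-training status nor form version is among the covariates.

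**The concern.** A sum over whichever questions were put to the child is workable for a single triage decision. As an outcome it has to mean the same thing for every child and at every visit. Here the number of items depends on a developmental state that can change during follow-up. Eligibility starts at age 0 (section 8.4), and the follow-up windows run to 6 and 12 months plus up to 4 months (section 6.4), so some children may answer the short form at baseline and the long form later.

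Three things are at stake for this outcome: whether scores from the two forms can be pooled, whether the baseline score works as a covariate, and whether incomplete forms look healthier than complete ones. If the triage rule is not meant to carry over, the SAP leaves the score for a listed outcome undefined, and the choice could be made after the data are seen.

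**Working it through.** The SAP states no range, sample size or power for this score, so there is no figure of its own to reproduce. The inputs are the item counts and item points in section 11.7.

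**Range of each form**
- Not toilet trained (Q1-Q5): 2 + 4 × 2 = 10, so 0-10.
- Toilet trained (Q1-Q7): 2 + 6 × 2 = 14, so 0-14.

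**Effect of a change of form, Q1-Q5 held fixed**

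The raw sum rises by Q6 + Q7. Each is 0, 1 or 2, which gives 3 × 3 = 9 answer pairs:

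| Rise in points | 0 | 1 | 2 | 3 | 4 |
|---|---|---|---|---|---|
| Answer pairs | 1 | 2 | 3 | 2 | 1 |

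The total is unchanged only if both added answers are 'Never'. It rises for the other 8 pairs and cannot fall. These are counts of possible patterns, not proportions of children.

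Example: with Q1 = 0 and one point on every other item asked, the sum is 4 on the short form and 6 on the long form.

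**Baseline covariate**

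A baseline sum of 6 is 6/10 = 60.0% of the maximum on the short form and 6/14 = 42.9% on the long form. The section 11.9 model would treat the two as the same severity.

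**Skipped items**

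Summing completed questions gives a skipped item zero, so each skip lowers the total by whatever the answer would have scored, 0 to 2 points. The other instruments in section 11 handle this explicitly:
- PedsQL divides by the items answered and sets a 50% limit per subscale.
- WEMWBS uses the mean of the completed items for up to 3 missing.
- SDQ is prorated.
- ACT allows none missing.
- POEM scores a missing item as zero, but allows only one.

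The constipation score has no limit.

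**What the alternatives do**
- Five common items: the change on switching form, with Q1-Q5 fixed, is exactly 0.
- Percentage of maximum: both forms run 0-100%. The example above moves from 4/10 = 40.0% to 6/14 = 42.9%, and a child at the maximum on every item stays at 100% instead of going from 10 to 14. Movement is not abolished. With Q1-Q5 all zero and Q6-Q7 at their maximum, it goes from 0% to 4/14 = 28.6%. In the reverse case it goes from 100% to 10/14 = 71.4%. The shift can now go either way instead of only upward.

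**The case against.** The strongest reply is that the sum is expressly a triage rule. Neither section 11.7 nor section 11.9 says that it is the outcome score. That is correct, and it limits the point: carrying the sum over is an inference, made because no other rule is given. It does not remove the point, because the alternative is a listed outcome with no defined score, and the same amendment cures both.

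A reader might infer that any child who becomes toilet trained will look worse with unchanged symptoms. The documents do not support that. Two 'Never' answers add nothing. The wording of Q2-Q7 is not shown either, so points on the added items may report real constipation symptoms.

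A reader might also infer a bias against the intervention, if better treatment brings toilet training forward. Nothing in the SAP says that it does. Such a bias would be the between-arm difference in the proportion changing form, multiplied by the mean points added, and the SAP gives neither quantity. If form change simply follows age, randomised arms should be similar, and the age-group covariate may absorb part of the effect, although section 11.9 does not define the groups.

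Finally, this is one secondary outcome and plays no part in the sample size. That is a fair limit on its weight.

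**Conclusion.** The concern holds in a limited form. The only totalling rule in the SAP, if used for the outcome, mixes a 0-10 and a 0-14 scale, lets a change of form add 0 to 4 points with the same Q1-Q5 answers, mis-scales the baseline adjustment and counts skipped items as zero. The consequences supported by the document are non-comparability and noise in this one outcome. A directional bias is possible but not demonstrated.

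This rests on the assumption that the triage sum would be carried into the section 11.9 model. The number of children affected cannot be derived: the share not toilet trained at baseline is not stated, and the age restrictions for the tracer conditions (section 8.2) refer to an appendix file that is not shown. The amendment is worth making because it is cheap and concerns a listed outcome. The primary outcomes are not touched.

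**What to change.** Leave the triage sum in section 11.7 as it is, and add a separate outcome definition there:

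- Define the outcome score either as the five items asked of every child (0-10) or as the percentage of the maximum for the items answered. The five-item score removes the form effect completely. The percentage keeps all the items but leaves some movement in either direction.
- State the minimum number of items that must be answered for a score to be computed.
- Use the same definition at baseline, 6 months and 12 months, and for the baseline covariates in section 11.9.
- Report the 7-item score secondarily, in children toilet trained at both visits.
- If toilet-training status is used as a covariate, use baseline status only. Status at follow-up is measured after randomisation and could lie on the path of the treatment effect.

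The cost is SAP wording, since the answers come from the questionnaire already scheduled. The downside of the five-item option is that the two items asked only of toilet-trained children leave the main outcome score. The secondary 7-item report keeps them in view.

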11.8 A School & Work Absence questionnaire

- How many days of school has your child missed due to ill health or attending health-related appointments in the past three months?
 - Number of days
 - Other responses
 - My child is too young to attend school
 - My child is school age but does not attend school for health reasons
 - My child is school age but does not attend school for other reasons
 - I can't answer this question
- How many days of work have you missed in the past three months due to your child's illness or healthcare appointments?
 - Number of days
 - Other responses
 - I am not working because of my child's health needs
 - I am not working for other reasons
 - I can't answer this question

We will report the number of missing days, and also treat the outcome as binary (any absence or no absence). The binary outcomes will be analysed using logistic regression and with chi-squared tests.

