- provide informed consent for the evaluation team to 1) access their child's clinical details including a baseline clinical screening questionnaire which is completed on entry into the clinical service, and 2) have access to, and link, the child's GP and hospital data to assess the impact of CYPHP on both primary and secondary health service use. The baseline clinical screening questionnaire, completed for clinical services, includes the Strengths and Difficulties Questionnaire, and a condition-specific questionnaire: Asthma Control Test, GSTT Symptom Severity Measure (for constipation), or Patient Oriented Eczema Measure.
- complete an evaluation questionnaire at baseline (including health related quality of life measured by PEDSQL and CHU9D, and parental wellbeing measured by the Warwick-Edinburgh Mental Wellbeing Scale), and complete the clinical screening questionnaire and evaluation questionnaire at 6-month, and annual follow-up.
- give informed consent to be contacted to potentially participate in qualitative studies evaluating the service

Patient information sheets will make it clear that parents can consent or refuse consent to any of these components. Participants will be free to withdraw consent without prejudice at any time.

A parent/carer alone or with their child may be involved in the recruitment process. If the CYP is under 12 years of age the parent/carer will be asked to provide, on behalf of the child, informed consent, if they are happy to take part in the evaluation. If the CYP is between 12 and 16 years of age, the parent will be asked to provide informed consent and if the CYP is available at the time when parental consent is requested, the CYP will be asked to provide assent if they wish to participate.

TRACER CONDITION RECRUITMENT TIMELINE

Recruitment began in April 2018. The first participant was consented 22MAY2018, following their Health Check 24APR2018. Recruitment is planned to complete in December 2020.

POPULATION EVALUATION DATA

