6.4 Survey/questionnaire data from study database

Once the patient has consented to the study the participants will be asked to complete further questionnaires (listed below). These are described in section **Error! Reference source not found.**

- PedsQL
- CHU9D
- WEMWBS
- School & Work Absence Questions
 - How many days of school has your child missed due to ill health or attending health-related appointments in the past three months?
 - How many days of work have you missed in the past three months due to your child's illness or healthcare appointments?

Follow-up data is collected at 6 and 12 months (+ up to 4 months) following baseline data collection. At the follow-up time points the Health Check questionnaires are also repeated.

The schedule of events for the tracer condition analysis of CYPHP is displayed in Table 1.

Table 1: Schedule of data collection for CYPHP Tracer Condition Questionnaires

	Procedures	CYPHP Health Check	Baseline Study Questionnaires	CYPHP Service entry	6-month Follow-up Study Questionnaires	12-month Follow-up Study Questionnaires
Health Checks	ACT	C			C	C
	POEM	C			C	C
	Constipation questionnaire	C			C	C
	SDQ	X			X	X
	Social Questions	X			X	X
	Health Check Demographics	X				
Evaluation Questionnaires	Eligibility assessment		X			
	Informed consent		X			
	PedsQL		X (1° child outcome)		X (1° child outcome)	X (1° child outcome)
	CHU9D		X		X	X
	WEMWBS		X (1° parent outcome)		X (1° parent outcome)	X (1° parent outcome)
	School & Work Absence Questions		X		X	X
CYPHP Services	Offer of CYPHP Services			Requires registration with GP in intervention arm and clinical need identified at Health Check triage		
	Receipt of CYPHP Services			Receive service if: Parent/carer/CYP agrees and takes up service		

X: collected on all participants

C: collected on participants with the relevant condition

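### School absence is scored over a fixed three-month recall with no allowance for how many school days it contains; the likely cost is small, and a completion-period covariate deals with it cheaply

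*SAP*

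**What the plan says.** Section 11.8 of the SAP asks: "How many days of school has your child missed due to ill health or attending health-related appointments in the past three months". The other response options cover children too young for school, children not attending, and parents who cannot answer. None concerns school holidays, and nothing records or derives the school days available.

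On scoring, 11.8 states: "We will report the number of missing days, and also treat the outcome as binary (any absence or no absence"; and on analysis: "The binary outcomes will be analysed using logistic regression and with chi-squared tests". It names no model for the number of days.

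Section 11.9 gives the covariates for the questionnaire models. For each child the list reads: "Covariates at individual level: participant age group, sex, IMD 2015 quintile, IDACI 2015 quintile, Borough, and the baseline questionnaire outcome score". A second list, for the randomised groups of practices, starts with "Covariates at cluster level: mean IMD 2015, mean IDACI 2015, number of children under 16 years, rate of paediatric OP referrals 2015-16" and closes with the average baseline score in the group. Month, season and exposure are absent from both lists.

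On timing, section 5.2 says "Recruitment began in April 2018" and "Recruitment is planned to complete in December 2020". Section 6.4 says "Follow-up data is collected at 6 and 12 months (+ up to 4 months) following baseline data collection". Section 18.1 moves later follow-up back by the length of the pause (12 March to 4 July 2020) for those enrolled before it.

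**The concern.** Absence is an event count over time at risk, and here the time at risk is school days, not calendar days. Forms can be completed in any month, so two children with the same tendency to miss school can score differently only because one form looks back over the summer holiday and the other over the autumn term. The count and the any/none split are both affected, and the chi-squared test has no covariates that could absorb the difference.

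Elsewhere the SAP guards against this kind of problem. Section 7.1 uses annual rates for baseline health service use because of seasonality, and section 10.1 builds person-time denominators for rate outcomes. School absence has neither, and section 15 uses it again in the equity analyses.

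Three things are at stake: precision, the usefulness of the baseline absence score as a covariate, and, if completion months differ by arm, the validity of the comparison.

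**Working it through.** The SAP gives no absence rate, power statement or term calendar for this outcome, so there is no planned figure to reproduce. The sizes below rest on assumptions.

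**Assumed inputs.** An English-style school year from early September to late July, with half-term, Christmas and Easter breaks and a summer break of about six weeks: 196 school days. Recall window of 91 days. Constant absence rate of 5% of school days, with 2% and 8% as a range.

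**School days in the window**, counted for each of 365 completion dates:
- minimum 34 (late October), maximum 60 (early December)
- monthly means about 35 in September and October and 59 in December
- mean over the year 48.8, SD 8.0

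**Effect on one child's score** (rate × school days):
- 5%: 0.05 × 34 = 1.7 days against 0.05 × 60 = 3.0 days, a ratio of 60/34 = 1.76
- 2%: 0.68 against 1.20 days; 8%: 2.72 against 4.80 days

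**Probability of any absence at 5%, lowest against highest window:**
- independent days, 1 − 0.95^N: 0.83 against 0.95
- spells of 2.5 days, 1 − exp(−0.05N/2.5): 0.49 against 0.70
- negative binomial with dispersion 1, μ/(1 + μ): 1.7/2.7 = 0.63 against 3.0/4.0 = 0.75

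**Cost when timing is the same in both arms (5%, negative binomial, dispersion 1, forms spread evenly over the year).**
- Mean μ = 0.05 × 48.8 = 2.44; variance at a fixed window μ + μ² = 2.44 + 5.96 = 8.40.
- SD of μ from the calendar = 0.05 × 8.0 = 0.40, so its variance is 0.16. It enters twice (through the mean and through the dispersion term): 0.32.
- Extra variance 0.32/8.40 = 3.8%; standard error √1.038 = 1.019, so under 2%. A slightly different assumed calendar (mean 48.2, CV 0.16) gives 0.30/8.22 = 3.6%.
- Binary form, share of variance due to the calendar, Var(P)/[P̄(1 − P̄)] over the 365 dates: 0.7% (negative binomial), 1.7% (spells), 2.0% (independent days).

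**Baseline score as covariate**, ratio of school days in the follow-up window to those in the baseline window:
- 6 months on schedule: 35/60 = 0.58 to 60/35 = 1.71
- 12 months on schedule: 0.92 to 1.03
- 12 months plus the 114-day pause shift: 34/52 = 0.65 (baseline in mid-July) to 56/34 = 1.65 (baseline in late October)

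**If timing did differ by arm (illustration only).** If one arm had 10 percentage points more of its forms in September and October, drawn evenly from the year, its mean would shift by 0.10 × (35 − 48.8)/48.8 = −2.8% with no true effect.

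**The case against.** The comparison of interest is between arms. Both arms are recruited over the same period, followed on the same schedule and shifted by the same pause rule, and section 5.4 blinds the researchers involved in recruitment. Nothing in the SAP indicates that completion months differ by arm. This stands. A reader might infer from the 1.7 against 3.0 days that the arm comparison is biased, but that is a contrast between two extreme dates, not between arms. Large imbalance scenarios that move a fifth of an arm's forms from December to the autumn are not credible either: with even spread, December holds only about 8% of forms.

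A reader might also infer that neither follow-up can be set against baseline. That goes too far: an on-schedule 12-month form falls in the baseline season, and 11.8 plans no comparison of absence between time points. The mismatch applies at 6 months and to late or pause-shifted forms.

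The criticism should not assume a count model that 11.8 does not name; whether 11.9 covers the count is an inference. The work-absence item is not tied to term dates in the same way. An offset from published term dates would not remove seasonal illness and could misstate school days around the pause and lockdown. These points also stand, and they shape the fix. Finally, absence is not one of the primary outcomes.

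What the objection does not answer is that the listed covariates cannot absorb any timing difference that does arise. Families and services are unblinded, consent follows allocation, there are only 23 clusters, and follow-up may be four months late.

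**Conclusion.** The gap is real, but its expected harm is small. Sections 11.8 and 11.9 leave the school-absence score dependent on completion date, with up to a 1.76-fold difference between extreme dates under the assumed calendar. With similar timing by arm, this amounts to about 3.5 to 4% extra variance for the count at 5% absence, under 1% to about 2% for the binary form depending on how absences cluster, and a baseline score that adjusts poorly at 6 months. Bias in the arm comparison is possible but not shown.

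All sizes depend on the assumed term calendar, absence rate and distribution; the pattern itself needs only a long summer break. This is a low-cost improvement to a secondary outcome, not an error that threatens the trial's conclusions.

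**What to change.** For the school item only:

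1. In 11.8 and 11.9, add calendar period of completion (month or quarter, with year or a pause/lockdown indicator) as a covariate in the school-absence models. For on-schedule forms, follow-up month also largely fixes baseline month, so the same term deals with most of the baseline mismatch.
2. Make the adjusted logistic model the reported comparison for any absence, in place of the chi-squared test.
3. Tabulate completion month by arm at baseline, 6 and 12 months, so that readers can judge whether timing differed.
4. As a sensitivity analysis, derive the school days in each recall window from the form date and published term dates, exclude windows that overlap the pause or lockdown, and analyse days missed per school day with a log(school days) offset, with baseline absence expressed as the same rate.

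The cost is SAP wording, one derived variable and one table, with no new data collection. The drawbacks are a few extra covariates, and that borough term dates only approximate individual schools' calendars.

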5. SAMPLE SIZE, RECRUITMENT, RANDOMISATION, AND BLINDING

5.1 Sample size and power

Population Evaluation

Pseudo-anonymised data from all children (<16 years) within participating practices will be used to analyse the impact of the CYPHP Evelina London model on health service use.

11 clusters in each arm, and an average of 3800 CYP per cluster, provides over 87% power to detect a reduction of 20% in the rate of non-elective admissions, assuming a coefficient of variation of 0.142, as explained below.

The number of CYP per cluster is estimated conservatively based on the 89382 CYP (age 0-15) registered in 2015 in the GP practices in the 23 randomised clusters. For each financial year 2013-14 – 2015-16, the baseline rate of non-elective admissions and the coefficient of variation was estimated using counts of non-elective admissions per cluster from financial years 2013-14 – 2015-16, and counts of CYP enrolled per cluster during 2013-2015. The coefficient of variation used in the sample size calculation was the mean of these three estimates. The rate of non-elective admissions was the total rate estimated by combining data from the three financial years.

Tracer Condition Evaluation

With 11 clusters in each study arm, the study team will need to recruit a minimum of 1006 CYP with a long-term tracer condition (asthma, constipation or eczema) per arm (total 2012). This number of participants will give the study 90% power to detect a mean minimum clinically important difference (MCID) of 4.5 points (standard deviation 16.5) in the primary child-health outcome tool (parental reported PEDSQL (Varni et al, 1999),² as used previously with children with chronic health conditions such as asthma (Varni et al, 2004).⁸ Intraclass coefficient (ICC) is assumed to be 0.02 based on study of quality of life in children and young people with a related condition, hay fever (Hammersley et al, 2010). Inter-cluster variation is assumed to be (0.03) based on the harmonic mean and variance of cluster size derived from GP registrations. This number also accounts for a 30% loss to follow up.

In total there are **23 clusters**, 12 in one arm and 11 in the other. As such the outlined sample size underestimates the total power as we have assumed 11 clusters in each arm.

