15. EQUITY OF OUTCOMES ANALYSES

Some interventions, although they are beneficial overall, can widen inequality gaps. CYPHP aims to reduce inequality gaps.

Objective: To examine the impact of the CYPHP model of care on gradients (or variation) in health service use, physical and mental health, condition symptoms, health-related quality of life, parental well-being, and school/work absence.

To determine the impact of CYPHP on inequality gaps, we will examine differential intervention (moderator) effects, by adding an interaction term between measures of social disadvantage (listed below) and the study arm (intervention/control) variable, to the models estimating the impact of CYPHP on the study outcomes (listed below).

Measures of social disadvantage:

- IMD quintile (treated as ordered categorical variable)
- IDACI quintile (treated as ordered categorical variable)
- Ethnicity (Categories: White, Black, Asian, Mixed, Other)
- Health Check questionnaire responses regarding:
 - Housing concerns
 - Enough food for family

- Struggle to pay bills
- Parental mental health concerns

Outcomes: Health service use rates, PedsQL, CHU9D, ACT, POEM, Constipation, WEMWBS, SDQ, school/work absence

These will be explored with separate models, each model including one measure of disadvantage, as we expect these measures of disadvantage to be highly correlated. However, for ethnicity and parental mental health concerns, we plan to also adjust for socioeconomic status, to assess if there is an additional effect of these factors beyond their correlation with socioeconomic status, using IMD, IDACI, and/or a Health Check measure.

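### School and work absence is collected in days, but section 11.8 names tests only for any versus no absence; the day count has no stated model or effect measure, and neither form is named as the lead

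*SAP*

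**What the plan says.** Both absence items in SAP section 11.8 ask for a number of days: "How many days of school has your child missed due to ill health or attending health-related appointments in the past three months" and "How many days of work have you missed in the past three months due to your child's illness or healthcare appointments". Each puts illness and health appointments into one total.

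The handling follows in two sentences. The first is "We will report the number of missing days, and also treat the outcome as binary (any absence or no absence"). The second is "The binary outcomes will be analysed using logistic regression and with chi-squared tests".

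Section 11.9 then gives a rule for the questionnaire outcomes as a group: "Analysis (for 6-month and 12-month follow-up): Random-effects regression models", with individual-level and cluster-level covariates that include the baseline score. It excludes no outcome and names no distribution or link.

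Section 15 lists absence among the outcomes for the equity interaction models, "Outcomes: Health service use rates, PedsQL, CHU9D, ACT, POEM, Constipation, WEMWBS, SDQ, school/work absence", without saying whether days or any/none is meant.

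**The concern.** The day count holds more information than the cut at zero, and the SAP gives no reason for the cut. Under any/none, a child who goes from eight missed days to three is unchanged. Named tests attach only to that version. For the days, the analyst is left to choose the model, the effect measure and whether days or any/none is the main result. Elsewhere the SAP names a model to suit the data: Poisson for health service use counts (10.9) and logistic for the asthma quality indicators (12.2).

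The wording of the items adds a second difficulty. A single appointment day moves a family from none to any, whatever happens to illness days. The intervention arm receives clinical services beyond those of the control arm (4.2), so the two forms of the outcome need not move together.

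At stake is the reading of a family-level outcome that also feeds the equity analysis: a real fall in days lost could be presented as no effect.

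**Working it through.** **The plan's own figure.** The SAP states no power for absence. Section 5.1 sizes the consented sample on PedsQL: to "recruit a minimum of 1006 CYP with a long-term tracer condition (asthma, constipation or eczema) per arm (total 2012") for "90% power to detect a mean minimum clinically important difference (MCID) of 4.5 points (standard deviation 16.5"), with 11 clusters per arm, ICC 0.02 and 30% loss. Two-sided 5% is assumed.
- The cluster formula is c = 1 + (z_a + z_b)² × 2(s_w²/m + s_b²)/d².
- With s² = 272.25, s_b² = 0.02 × 272.25 = 5.445 and s_w² = 266.805, c = 11 gives m = 63.7 per cluster.
- That is 700 analysed per arm, and 700/0.7 = 1000 recruited against the stated 1006.

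The figure reproduces. It supplies only the sample size and ICC used below.

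**Effective sample per arm**, n/[1 + (n/11 − 1) × 0.02]:
- All followed up: 1006 × 0.7 = 704, so 704/2.26 = 311.5.
- 60% able to answer (school age, or parent working; an assumption): 422, so 422/1.747 = 241.5.

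**Assumed absence data.** Days are negative binomial with mean μ of 1, 2, 4 or 6 and dispersion k of 0.5, 0.8 or 1.5. The intervention multiplies mean days by 0.8. Baseline adjustment is ignored for both tests.
- Any/none: P(any) = 1 − (1 + μ/k)^(−k) in each arm, then a Wald test of two proportions.
- Count: z = |ln 0.8| / √[(1/μ + 1/k + 1/(0.8μ) + 1/k)/n_eff].

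**One case in full** (μ = 4, k = 0.8, n_eff = 241.5):
- Any/none: 76.15% against 72.41%, a difference of 3.74 points, SE 3.97 points, z = 0.94, power 15%.
- Count: variance (0.25 + 1.25 + 0.3125 + 1.25)/241.5 = 0.01268, SE 0.1126, z = 0.2231/0.1126 = 1.98, power 51%.

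**Across k, at n_eff = 241.5:**

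| Mean days | Any/none power | Count power |
|---|---|---|
| 1 | 16–28% | 28–45% |
| 2 | 14–27% | 33–60% |
| 4 | 12–20% | 37–71% |
| 6 | 11–16% | 38–76% |

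Compared setting by setting, the count model gains 12 to 17 points at a mean of 1 day and 19 to 60 points at means of 2 to 6. At n_eff = 311.5 and means of 2 to 6 the gain is 24 to 66 points.

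**Appointment days.** Suppose illness days fall by 25% and 15% of intervention children gain one appointment day. Then P(any) = 1 − 0.85 × (1 + 0.75μ/k)^(−k), and the mean is 0.75μ + 0.15.
- μ = 4, k = 0.8: mean days fall from 4.00 to 3.15, while any absence goes from 76.2% to 1 − 0.85 × 0.2875 = 75.6%. Simulated power at effective n 240 is about 5% for any/none and 59% for mean days.
- μ = 2, k = 0.5: mean days fall from 2.00 to 1.65, while any absence rises from 55.3% to 1 − 0.85 × 0.5 = 57.5%.

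**Where the ranking reverses.** If the only effect is to move 15% of children to zero days (μ = 4, k = 0.8, effective n 240), simulated power is about 78% for any/none and 27% for mean days. A separate simulation used 704 per arm, no clustering and a 15% relative cut in having any absence. Any/none had 66%, 93% and 99.9% power against 33%, 55% and 73% for mean days, at 40%, 60% and 80% with any absence.

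**The case against.** A reader might infer that any/none is the only formal analysis planned for absence. The text does not establish that. Section 11.8 says the binary form is used as well as the number of days, and 11.9 excludes no questionnaire outcome. CHU-9D, WEMWBS, SDQ, ACT, POEM and the constipation score have no model in their own subsections either and rely on 11.9. The logistic sentence may be there only because a binary outcome departs from the default. This objection stands: the day count may be covered. It does not close the gap, because 11.9 gives no distribution, link or effect measure for a skewed count with zeros, and neither form is ranked first.

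A reader might also infer that the cut discards most of the power. The SAP has no absence mean, spread or share of zeros to support that as a general statement. At a mean of 1 day the loss is smaller, and for an effect confined to becoming absence-free any/none is the stronger test. The count model's own power is also modest in many settings.

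Nor do the documents show that appointments will reverse the result. Section 4.2 describes in-reach clinics as typically replacing a hospital outpatient referral, and some targeted care takes place at home. The 15% gaining a day is an assumption. If most children already miss a day, few can move from none to any. Because the days will be reported, a fall would not be wholly hidden. The reversal is possible, not demonstrated.

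**Conclusion.** The point holds as a gap in specification with a better method readily available. Named tests exist only for any/none, the day count has no count model or effect measure under either reading of 11.9, and no lead analysis is stated.

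For a 20% proportional fall in days at an effective sample of about 242 per arm, any/none has roughly 11% to 28% power against 28% to 76% for a count model. This rests on assumed negative binomial counts, a proportional effect, 60% able to answer, and the PedsQL ICC of 0.02 applied to absence. In the cases run, any/none was clearly stronger only when the effect was confined to having any absence at all. Mixing appointment and illness days means any/none could miss or contradict a fall in days lost, under assumptions the SAP neither supports nor rules out.

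Section 15 does not commit the equity models to the binary form; it leaves the form open. PedsQL and WEMWBS are the primary outcomes in the consented group and absence is not, so the priority is moderate.

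**What to change.** In 11.8, state for school and for work separately that days missed in the past three months, at 6 and 12 months, are the lead absence analysis. Use a random-effects negative binomial model with a GP cluster random effect and the 11.9 covariates, including baseline days. Report a rate ratio with 95% CI, and add a capped or robust sensitivity check for very high counts.

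Keep any versus none as a supportive analysis with the same covariates and cluster effect; a plain chi-squared test takes no account of clustering. In section 15, state that the absence interaction models use the day count.

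The cost is a few sentences and two additional models on data already collected. The count model is less sensitive to an effect confined to becoming absence-free, which the retained any/none analysis covers.
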